## MODIFICATION HISTORY

Listed below are modifications made to the SAP after the signed approval(s).

Unique Identifier for this Version	Date of the Document Version	Author	Significant Changes from Previous Authorized Version
1.0	30SEP2022	[REDACTED]	Not Applicable – First Version

---

Document: BI\_1297-0015\_SAP\_Final\_v1.0  
Author: [REDACTED]

Version Number: Final 1.0  
Version Date: 30Sep2022

Template No: CS\_TP\_BS016 – Revision 7  
Effective Date: 01Nov2021

Reference: CS\_WI\_BS005

---

## 1. INTRODUCTION

As per ICH E9, the purpose of this document is to provide a more technical and detailed elaboration of the principal features of the analysis described in the protocol, and to include detailed procedures for executing the statistical analysis of the primary and secondary variables and other data. This trial statistical analysis plan (TSAP) assumes familiarity with the Clinical Trial Protocol (CTP), including Protocol Amendments. In particular, the TSAP is based on the planned analysis specification as written in CTP Section 7 "Statistical Methods and Determination of Sample Size". Therefore, TSAP readers may consult the CTP for more background information on the study, e.g., on study objectives, study design and population, treatments, definition of measurements and variables, planning of sample size, randomization.

This document describes the rules and conventions to be used in the presentation and analysis of safety, pharmacokinetics (PK) and [REDACTED] data for Protocol 1297-0015. It describes the data to be summarized and analyzed, including specifics of the statistical analyses to be performed.

This TSAP is based on protocol version 1.0, dated 26 November 2021.

This TSAP is developed using the [REDACTED] statistical analysis plan templates. The operating procedures (SOPs) and programming standards of the Sponsor will be followed for this study.

## 2. STUDY OBJECTIVES

### 2.1. PRIMARY OBJECTIVE

The main objective of this trial is to investigate the relative bioavailability of 40 mg BI 695501 100 mg/mL (test) versus 40 mg BI 695501 50 mg/mL (reference) following single subcutaneous administration.

### 2.2. FURTHER OBJECTIVES

Further objectives are the evaluation and comparison of additional pharmacokinetic parameters between the treatments and assessment of safety and tolerability.

## 3. STUDY ENDPOINTS

### 3.1. PRIMARY ENDPOINTS

The following pharmacokinetic parameters will be determined for 40 mg BI 695501 100 mg/mL and 40 mg BI 695501 50 mg/mL:

Document: BI\_1297-0015\_SAP\_Final\_v1.0  
Author: [REDACTED]

[figure not shown]
Version Number: Final 1.0  
Version Date: 30Sep2022

Template No: CS\_TP\_BS016 – Revision 7  
Effective Date: 01Nov2021

Reference: CS\_WI\_BS005

[figure not shown]
- $AUC_{0-1344}$  (area under the concentration-time curve of the analyte in plasma over the time interval from 0 to 1344 hours after dose administration)
- $AUC_{0-\infty}$  (area under the concentration-time curve of the analyte in plasma over the time interval from 0 extrapolated to infinity)
- $C_{\max}$  (maximum measured concentration of the analyte in plasma)

### 3.2. FURTHER ENDPOINTS

Safety and tolerability of 40 mg BI 695501 100 mg/mL and 40 mg BI 695501 50 mg/mL will be assessed based on:

- Adverse events (including clinically relevant findings from the physical examination or 12-lead ECG)
- Safety laboratory tests
- Local tolerability
- Vital signs (BP, PR)

Document: BI\_1297-0015\_SAP\_Final\_v1.0  
Author: 

Version Number: Final 1.0  
Version Date: 30Sep2022

Template No: CS\_TP\_BS016 – Revision 7  
Effective Date: 01Nov2021

Reference: CS\_WI\_BS005

---

## 4. STUDY DESIGN

### 4.1. GENERAL DESCRIPTION

The trial will be performed as a randomized, single-dose, double blind, parallel arm trial in healthy male and female subjects aged  $\geq 18$  to  $\leq 55$  years.

It is planned to include 200 healthy male and female subjects into the trial to ensure at least 190 subjects for the primary analysis. Subjects will be randomly assigned to receive one dose of either BI 695501 40 mg/0.4 mL (T) or BI 695501 40 mg/0.8 mL (R). All study drugs will be administered by subcutaneous injection.

The trial will consist of a Screening period of up to a maximum of 28 days. The subject will check-in to the trial center on Day -1, will be dosed on Day 1. All subjects will remain in the clinic until day 2 after dosing. The subject will then return to the clinic for 13 ambulatory visits on Days 3, 4, 5, 6, 7, 8, 10, 15, 22, 29, 36, 43 and 57 (e.o.t.).

Additionally, all AEs, regardless of relatedness, will be collected until 10 weeks after the administration of trial medication. Adverse events not fully resolved at the Safety Follow-up visit will be followed until recovery or in case of persistency, sufficient characterization has been achieved and the investigator and medical monitor agree to not pursue them further.

### 4.2. SCHEDULE OF EVENTS

Schedule of events can be found in Section 6.1 and 6.2 of the protocol.

### 4.3. CHANGES TO ANALYSIS FROM PROTOCOL

There are no changes in the analysis plans relative to the study protocol.

---

## 5. PLANNED ANALYSES

### 5.1. INTERIM ANALYSIS

There are no formal interim analyses planned for this study.

---

Document: BI\_1297-0015\_SAP\_Final\_v1.0  
Author: [REDACTED]

Version Number: Final 1.0  
Version Date: 30Sep2022

Template No: CS\_TP\_BS016 – Revision 7  
Effective Date: 01Nov2021

Reference: CS\_WI\_BS005

## 5.2. FINAL ANALYSIS

All final, planned analyses identified in this TSAP will be performed by [REDACTED] Biostatistics (excluding PK descriptive analysis) and by BI (responsible for PK descriptive analyses and PK Tables, Listings, and Figures (TLFs) related to descriptive analysis) following sponsor authorization of this Statistical Analysis Plan, determination of analysis sets, database lock and unblinding of treatment.

## 6. ANALYSIS SETS

Agreement and authorization of subjects included/ excluded from each analysis set will be conducted by BI during the report planning meeting prior to the database lock of the trial.

### 6.1. ALL SUBJECTS ENROLLED SET [ENR]

The all subjects enrolled set will contain all subjects who provide informed consent for this study. Subjects in this population will be used for disposition summaries.

### 6.2. ALL SUBJECTS RANDOMIZED SET [RND]

The all subjects randomized set will contain all subjects in the ENR set who were randomized to trial medication.

For analyses and displays based on RND, subjects will be classified according to randomized treatment.

### 6.3. SAFETY ANALYSIS SET [SAF]

The safety analysis set will contain all subjects who were randomized and treated with study drug and will be analyzed according to treatment received. Subjects in this population will be used for all safety, dosing and demographic summaries.

### 6.4. PHARMACOKINETIC ANALYSIS SET [PKS]

The Pharmacokinetic Set (PKS) will consist of all randomized subjects who receive the single dose of trial medication, and have at least one evaluable primary PK parameter, and are without important protocol deviations or violations thought to have a relevant impact on the PK of BI 695501.

Pharmacokinetic parameters for a subject will be included in the analysis unless the subject has an important protocol violation relevant for the evaluation. Whether a protocol violation is relevant will be

Document: BI\_1297-0015\_SAP\_Final\_v1.0  
Author: [REDACTED]

Version Number: Final 1.0  
Version Date: 30Sep2022

Template No: CS\_TP\_BS016 – Revision 7  
Effective Date: 01Nov2021

Reference: CS\_WI\_BS005

decided no later than in the report planning meeting.

Reasons for exclusion of single pharmacokinetic parameters may include (but are not limited to):

- Relevant time deviations
- Use of restricted medications
- Dosing errors
- Missing samples relevant for correct estimation of PK parameters Cmax or AUC

It will also be decided in the report planning meeting which subjects are to be excluded from the PKS. Important protocol violations will be defined before the final database lock.

In case of PK profiles suggesting biologically implausible results for subcutaneous administration or suggesting extreme values (high or low), then these values and/or profiles will be excluded from the PK evaluation.

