7.2.1.1 Pharmacokinetics

The pharmacokinetic parameters listed in Section 2.1 [REDACTED] for drug BI 695501 will be calculated according to the relevant procedures of the Sponsor.

Pharmacokinetic parameters of a subject will be included in the analysis unless the subject has an important protocol violation relevant for the evaluation. Reasons for exclusion of single pharmacokinetic parameters can for example be:

- Time deviations
- Use of restricted medications
- Dosing errors

Whether a protocol violation is important will be decided no later than in the Report Planning Meeting. It will also be decided in the Report Planning Meeting which subjects are to be excluded from the PKS. Subjects who are not included in the PKS (refer to Section 7.2.1) will be reported with their individual plasma concentrations and individual PK parameters;

Proprietary confidential information © 2021 Boehringer Ingelheim International GmbH or one or more of its affiliated companies

however, they will not be included in descriptive statistics for plasma concentrations, PK parameters or other statistical assessments.

In case a pre-dose concentration value is greater than 5% of Cmax, the subject's PK data will not be included in any statistical evaluations, in accordance with international guidance. The individual PK parameters of such a subject will be calculated and listed separately. If a predose concentration is above the limit of quantification, but less than or equal to 5% of the subject's Cmax value, the subject's data without any adjustments will be included in all PK measurements and calculations.

Details of the analysis and presentation of PK data will be provided in the Trial Statistical Analysis Plan (TSAP).

Only concentration values within the validated concentration range and actual sampling times will be used for the calculation of pharmacokinetic parameters. Concentrations used in the pharmacokinetic calculations will be in the same format provided in the bioanalytical report, (that is, to the same number of decimal places provided in the bioanalytical report).

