7.3.2 Pharmacokinetics

Handling of missing PK data will be performed according to the relevant procedures of the Sponsor.

Drug concentration data identified with NOS (no sample available), NOR (no valid result), NOA (not analysed) will not be considered for the non-compartmental analysis and the creation of graphs, except for concentration values in the lag phase identified as BLQ which will be set to zero. The lag phase is defined as the period between time zero and the first time point with a concentration above the quantification limit.

Descriptive statistics of parameters are calculated only when a parameter value is available for at least 2/3 of the treated individuals. If the actual sampling time is not recorded or is missing for a certain time point, the planned time will generally be used for this time point instead. PK parameters that cannot be determined will be identified as “not calculated”.

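### SAP 6.4 requires extreme PK values to be removed from the primary analysis, with no cut-off, no required cause, and no counterpart in the protocol

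*SAP*

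**What the plan says.** Protocol 7.2.1.1 sets the general rule: "Pharmacokinetic parameters of a subject will be included in the analysis unless the subject has an important protocol violation relevant for the evaluation". Its examples of reasons are time deviations, restricted medication and dosing errors. The protocol's other exclusions have defined triggers:

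- a pre-dose concentration above 5% of Cmax (7.2.1.1);
- concentrations outside the assay's range: "Only concentration values within the validated concentration range and actual sampling times will be used for the calculation of pharmacokinetic parameters" (7.2.1.1);
- missing or invalid results: "Drug concentration data identified with NOS (no sample available), NOR (no valid result), NOA (not analysed) will not be considered" (7.3.2).

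SAP 6.4 repeats the general rule and adds one further reason, "Missing samples relevant for correct estimation of PK parameters Cmax or AUC". It then ends with a separate rule with two triggers joined by *or*. The first is a profile that is biologically implausible for subcutaneous dosing. The second is a profile "suggesting extreme values (high or low), then these values and/or profiles will be excluded from the PK evaluation".

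SAP 4.3 states: "There are no changes in the analysis plans relative to the study protocol". On timing, SAP 6 says "Agreement and authorization of subjects included/ excluded from each analysis set will be conducted by BI during the report planning meeting", before database lock. SAP 5.2 places the final analyses after "determination of analysis sets, database lock and unblinding of treatment".

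**The concern.** Implausibility is named separately, so the word *extreme* must reach values that are plausible but far from the rest. A very high or very low AUC is an outcome, not a protocol violation. The closing sentence of SAP 6.4 therefore conflicts with Protocol 7.2.1.1 and with the rule stated earlier in SAP 6.4 itself. It also makes the no-change statement in SAP 4.3 inaccurate on this point.

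The trial exists to estimate T/R and its 90% CI for AUC and Cmax. Selecting data on those same variables can do three things:

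- remove ordinary data, which understates the residual variability and narrows the CI;
- pull T/R toward 1 when the true ratio is not 1, even with a blinded pooled cut;
- erase a real difference if unusual exposures are more frequent with one formulation, which a formulation comparison ought to show.

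**Working it through.** **Inputs from the documents.** 190 evaluable subjects (Protocol 3.1 and 7.5), 1:1 allocation (7.4), hence 95 per arm; two-sided 90% CI on the log scale (7.2.2); gCV 25-54% in earlier trials (7.5).

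**Assumed.** Log-normal data and every cut-off, because the SAP gives none.

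**The plan's own table first.** With sigma = sqrt(ln(1 + gCV²)), the precision in Table 7.5:1 is

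exp[ t(0.95; 188) × sigma × sqrt(2/95) × sqrt(chi²(0.95; 188)/188) ] = exp[ 1.653 × sigma × 0.1451 × 1.0842 ].

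For gCV 25, 40 and 50%, sigma is 0.2462, 0.3853 and 0.4724, giving 1.066, 1.105 and 1.131. All three match the table, so the variability model below is the plan's own.

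**How often clean data look extreme.** In simulated trials with nothing wrong, using the pooled sample mean and SD, the chance that at least one of 190 values falls outside is 93% at 2.5 SD and 39% at 3 SD.

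**Effect on variability.** Cutting a normal distribution at ±2, ±2.5 or ±3 SD multiplies its SD by 0.880, 0.955 or 0.987. Allowing for the subjects lost (about 8.5, 2.2 and 0.5), the CI width changes by about

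- 2 SD: 0.880 × sqrt(190/181.5) = 0.90, so 10% narrower;
- 2.5 SD: 0.955 × sqrt(190/187.8) = 0.96, so 4% narrower;
- 3 SD: 0.987 × sqrt(190/189.5) = 0.99, so 1% narrower.

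In simulation, a true gCV of 50% is reported as about 43.5%, 47.6% and 49.3%.

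**Effect on T/R, equal tails.** Two-group log-scale comparison, pooled blinded cut, 20,000 simulated trials per cell, gCV 25-54%, true T/R 1.10:

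| Cut (assumed) | Mean dropped | Estimated T/R | Coverage of 90% CI |
|---|---|---|---|
| 2 SD, log scale | 8.5 | about 1.078 | 83-89% |
| 2.5 SD, log scale | 2.2 | 1.092 | 88-90% |
| 3 SD, log scale | 0.5 | 1.098 | about 90% |
| 1.5 × IQR, untransformed | 3.6-7.5 | 1.084-1.090 | 88-90% |

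With a true T/R of 1.00 the estimate stays at 1.00 and coverage near 90% at every cut.

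**Same check with the planned model.** ANCOVA with treatment, location and weight (assumed: weight explains 20% of the variance, location effect 10%), true T/R 1.10: 2 SD gives 1.082-1.083 with coverage 84-89%; 3 SD gives 1.098-1.100 with 90%.

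**Effect on T/R, unequal tails.** Assume each test subject has a 3% chance (about 3 of 95) of one third of the usual exposure and the ratio is otherwise 1. The true geometric mean ratio is exp(0.03 × ln(1/3)) = 0.968. The mirror case, three times the exposure, gives exp(0.03 × ln 3) = 1.034. With a blinded pooled 3 SD cut:

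| gCV | Low tail, true 0.968: estimate (coverage) | High tail, true 1.034: estimate (coverage) |
|---|---|---|
| 25% | 0.995 (80%) | 1.005 (79%) |
| 40% | 0.982 (89%) | 1.019 (89%) |
| 50% | 0.976 (about 90%) | 1.023 (about 90%) |

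At gCV 25% most of a real formulation difference disappears although nobody is unblinded.

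**The case against.** **The text.** The trigger speaks of profiles, so it may mean a pharmacokineticist's review of concentration curves and not a statistical cut on AUC or Cmax. The protocol's reasons are only examples, the SAP's list is open, and Protocol 7.2.1.1 leaves PK detail to the TSAP, so the clause could be read as delegated detail. A definition may sit in the sponsor's SOP, or in the section 7.2.1.2 to which Protocol 7.2.1 refers but which is not in the text available.

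The consequence nevertheless covers single values as well as profiles. The examples stand under a sentence that requires a protocol violation, and delegating detail does not turn an extreme outcome into one. The possible unseen definition does stand as a limit: the claim is only that the SAP itself states no cut-off and no cause.

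**The size.** A 2 SD cut would discard about 8.5 ordinary subjects per trial, nearly the whole allowance of 10 non-evaluable subjects, and few would call such values extreme. At 3 SD with equal tails the effect is small, and at 4 SD it vanishes. The unequal-tail case is assumed, and its clear loss of coverage appears only at the bottom of the gCV range. A low exposure from a faulty injection might already count as a dosing error. All of this stands, and it limits the size.

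**The safeguards.** Analysis sets are fixed before lock and unblinding. Subjects outside the PKS are still listed individually (Protocol 7.2.1.1) and set sizes are tabulated (SAP 10). There is no acceptance range (Protocol 7.1), so no pass or fail can be tipped. These points limit treatment-directed selection and make subject-level exclusions visible. They do not prevent the effects above, which arise under a fully blinded cut, and the SAP does not expressly say when single values are removed.

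**The remedy.** Biological implausibility has no cut-off either, so the same profile could be dropped under that label. That is fair, and it is why the fix asks for a documented, blinded reason.

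**Conclusion.** The point holds and should be fixed. SAP 6.4 contains a mandatory, outcome-dependent exclusion in the primary analysis that the protocol does not contain and SAP 4.3 does not declare.

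Its size cannot be fixed, because the cut-off is not given. Under the assumed cuts it ranges from negligible (3 SD or wider, equal tails) to a T/R of about 1.08 in place of 1.10, with coverage as low as 83% (2 SD, gCV 25%). If extreme exposures are real and more frequent in one arm, a blinded 3 SD cut can hide most of the difference at gCV 25%, with coverage near 80%. If the true ratio is 1 and the tails are equal, the harm is confined to understated variability. Because the trial is designed for estimation, the harm falls on the estimate and its interval, not on a decision rule.

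**What to change.** - In SAP 6.4, delete the extreme-value trigger, so that extremeness alone is not a reason for exclusion from the primary ANCOVA.
- Keep every other stated ground: important protocol violations (relevant time deviations, restricted medication, dosing errors), missing samples that matter for Cmax or AUC, pre-dose above 5% of Cmax, the validated range, NOS/NOR/NOA results, and biologically implausible profiles.
- Add one sentence: implausible profiles or single values are excluded while blinded, before database lock, with the reason documented.
- Show any analysis without extreme values only as a labelled sensitivity analysis.
- In SAP 4.3, declare every exclusion ground that goes beyond the protocol.

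The cost is two SAP edits and one optional sensitivity run. The primary CI may be slightly wider.

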## 7. GENERAL CONSIDERATIONS

Derivation of the PK parameters for BI 695501 in plasma, and the PK summaries and data listings, will be the responsibility of the clinical pharmacokineticist at BI. The safety and [REDACTED] summaries and data listings will be the responsibility of the study biostatistician at [REDACTED].

Some minor modifications may be necessary to the planned design of tables, figures, and listings to accommodate data collected during the actual study conduct

### 7.1. SUMMARY STATISTICS

For qualitative variables, the population size (N for sample size and n for available data) and the percentage (of available data) for each class of the variable will be presented. Quantitative variables will be summarized using descriptive statistics, including n, mean, standard deviation (SD), median, interquartile range (IQR calculated as third quartile [Q3] minus first quartile [Q1]), minimum, and maximum values. In addition, 10th percentile (P10), 90th percentile (P90), coefficient of variation (CV%), geometric mean (gMean) and geometric CV% (gCV%) will also be presented for PK concentration data and all PK parameters, where applicable.

### 7.2. TREATMENT SUMMARIZATION

In general, data will be presented for each treatment group. Data for all study subjects combined will also be presented when appropriate.

---

Document: BI\_1297-0015\_SAP\_Final\_v1.0  
Author: [REDACTED]

Version Number: Final 1.0  
Version Date: 30Sep2022

Template No: CS\_TP\_BS016 – Revision 7  
Effective Date: 01Nov2021

Reference: CS\_WI\_BS005

## 7.3. PRECISION

Safety variables (ie, clinical laboratory values, and vital signs), including derivations thereof, will be reported to the same precision as the source data.

For the reporting of descriptive statistics, the minimum and maximum values will be presented to the same precision as the source data (base precision); base precision+1 for the mean, median and confidence intervals (CIs); and base precision+2 for the SD and IQR (see APPENDIX 1). Percentages will be presented with one decimal point.

Only PK concentration values within the validated concentration range and actual sampling times will be used for the calculation of pharmacokinetic parameters. Concentrations used in the pharmacokinetic calculations will be in the same format as in the bioanalytical report (that is to the same number of decimal places provided in the bioanalytical report).

For the reporting, individual and descriptive statistics of PK concentrations and parameters will be presented with three significant digits. Descriptive statistics includes N, gMean, gCV%, mean, CV%, SD, minimum, P10, Q1, median, Q3, P90 and maximum. P-values, if any, shall be reported according to the convention described in APPENDIX 1.

## 7.4. REFERENCE START DATE AND STUDY DAY

Study Day will be calculated from the reference start date, and will be used to show start/stop day of assessments and events.

Reference start date is defined as the day of study medication administration, (Day 1 is the day of the study medication administration), and will appear in every listing where an assessment date or event date appears.

- If the date of the event is on or after the reference start date then:

Study Day = (date of event – reference start date) + 1.

- If the date of the event is prior to the reference start date then:

Study Day = (date of event – reference start date).

In the situation where the event date is partial or missing, Study Day, and any corresponding durations will appear partial or missing in the listings.

